3.3 Primary Endpoint

The primary endpoint (definition below) of the study is a within-subject comparison of tremor power before stimulation to after stimulation, as captured by the Cala Trio device’s on-board accelerometer. Unless otherwise specified, “tremor frequency”, “tremor power” and “single-session kinematic response” are per-session metrics defined as follows:

- “Tremor frequency” is the frequency, in the 3 – 12 Hz range associated with Parkinson’s tremor, where the power spectral density (PSD) of a session’s pre-stimulation accelerometry data is largest.
- “Tremor power” is integral of the PSD of the tremor accelerometry data in the 3 Hz window centered on the session’s tremor frequency.

- “Single-session kinematic response” is defined as the pre-stimulation tremor power divided by the post-stimulation tremor power.

The primary endpoint, “kinematic response”, is defined as the per-patient median of single-session kinematic responses.

Patients will be included in the primary endpoint analysis only if they completed at least 10 therapeutic sessions that met the following data quality criteria:

- Session was started at least 2 hours after the completion of a previous session.
- Participant completed both pre- and post-stimulation motion recordings, that are each
 - sufficiently free of recording artifact, including accelerometer saturation
 - sufficiently free of motion artifact, as detected by excessive power outside the 3 – 12 Hz tremor range in the PSD.

Statistical testing of the primary endpoint will be based on the cohort of all enrolled subjects for whom outcome data are available. The statistical objective related to the primary endpoint is to demonstrate that action hand tremor severity in PD is reduced with the Cala Trio device. Formally, the null and alternative hypotheses to be tested for the primary endpoint is as follows:

$$H_0: M_T \geq 1$$

$$H_A: M_T < 1$$

where M_T is the median kinematic response captured over the 4-week study.

The primary endpoint is a continuous variable and will be summarized descriptively using log-transformed mean and standard deviation, median, and interquartile range (first and third quartiles). Hypothesis testing of the change score M_T will be performed using Wilcoxon’s signed-rank test.

The primary endpoint is met if the two-sided p-value is < 0.05 , such that the null hypothesis is rejected in favor of the alternative hypothesis. The study is successful if the primary endpoint is met.

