2.1.2 Stimulator

The stimulator contains the electronics for providing TAPS and was designed with careful considerations of use by subjects with hand tremors. There are 3 easy-to-press buttons (Figure 1) on the stimulator that are used for calibration and stimulation amplitude adjustment, among other functions. Text prompts, stimulation delivery parameters, and other messages are provided on a full color display to provide instructions and stimulation delivery information to the clinician and subject throughout device use. A countdown timer automatically terminates the delivery of stimulation after a 40-minute treatment session. The stimulator is powered by a rechargeable battery, which can be recharged through the base station (see additional details below). The stimulator produces charge-balanced, current-controlled, biphasic, square waveforms. The duration of the primary (depolarizing) phase is 300 μ sec, the frequency is 150 Hz, and the maximum current is 8 mA. The current is delivered to alternating electrode pairs in the band that target the median and radial nerves of the subject. The stimulation alternates between electrode pairs at the subject's tremor frequency (4 - 12 Hz), which is measured during a calibration procedure while the subject performs a tremor-inducing task. The tremor frequency is measured by motion sensors contained within the stimulator which gather kinematic data.

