2 STUDY OVERVIEW

2.1 Design and Objective

This is a prospective, single-site, single-arm, non-significant risk study designed to evaluate the Cala Trio device for action tremor in PD. Subjects will be screened for eligibility and fitted with a Cala Trio device. Subjects will wear the device at home for a period of 4 weeks, during which they will be asked to stimulate their dominant hand twice daily. The stimulation amplitude will be based on each subject's stimulation threshold. Subjects will have in-clinic assessments at enrollment, as well as before and after treatment of 4 weeks. The study timeline, reproduced from the study protocol, is illustrated below. More detail on study data follows below.

All subjects will be informed of their right to withdraw from the clinical study at any time without penalty or loss of benefits. The Investigator may prematurely discontinue any subject from the study if the Investigator feels that the subject can no longer fully comply with the requirements of the study or if any of the study procedures are deemed potentially harmful to the subject.

The study objective is to evaluate symptomatic hand tremor relief in the treated hand following stimulation with the Cala Trio device in adults with action tremor in PD over a duration of 4 weeks.

a. Visit 1

Subjects will be reminded to be in the *off* state, i.e., to skip their last dose of PD medication, prior to their telemedicine Visit 1. The following assessments will occur:

- Screening activities including medication review and medical history. No medical records will be used for this study, so all eligibility criteria will be based upon self-reported information from each subject and verification by qualified study staff.
- Tremor assessments (while in the *off* state) including:
 - Modified MDS Unified Parkinson's Disease Rating Scale Part III (MDS-UPDRS) to confirm eligibility will be rated by the PI
 - Bain & Findley Activities of Daily Living (BF-ADL) upper limb subset score will be rated by the subject based on their recall of the previous week (no props will be used)
- Demographic information, Parkinson's clinical characteristics, and wrist size and handedness will be collected based on self-reported information from subjects.

Once a subject has been confirmed to be eligible for the study, a device kit containing a stimulator, base station and band will be shipped directly to the subject's home ahead of Visit 2.

b. Visit 2

Visit 2a

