Once a subject has received the device kit, device training will occur via telemedicine, as follows:

Positioning and Fastening Cala Trio

Prior to device positioning, subjects should dampen the wrist of the prescribed hand to ensure good connection between the electrodes and wrist. Subjects should position the device on the prescribed hand such that the electrodes are positioned over the median and radial nerves, and securely tighten the band.

Device Calibration

To calibrate the Cala Trio device, subjects will perform a series of postural hold tremor tasks, in which the device measures the subject's tremor frequency and sets the stimulation burst frequency based on the measured tremor frequency.

For the purposes of this study, only the outstretched postural hold tremor task will be used.

Setting Stimulation Intensity

The subject will set the stimulation intensity to an amount they can comfortably tolerate while doing light activities. Paresthesia should be perceived in the parts of the hand and/or fingers innervated by the median and radial nerves. The stimulation intensity selected during the initial amplitude calibration is saved on the device for subsequent sessions. The subject can decrease or turn off the stimulation at any point in time and may adjust their stimulation intensity from session to session to maintain the minimum paresthesia threshold.

Device Training

During the course of the visit, study personnel will instruct the subject on proper use of the device. Subjects must demonstrate competence to operate the device and comprehension of the instructions for use prior to completing the training.

Visit 2b

Once a subject is trained on the device, the subject will receive a single 40-minute therapy session with their Cala Trio. The subject will be asked to not stimulate at least 8 hours prior to this visit. The following assessments will be made prior to the therapy session and again immediately post the therapy session:

- Tremor assessments (while in the *off* state) including:
 - Modified MDS Unified Parkinson's Disease Rating Scale Part III (MDS-UPDRS) will be rated by the PI
 - Bain & Findley Activities of Daily Living (BF-ADL) upper limb subset score will be rated by the subject. The BF-ADL assessment will be performed using the subject's own household props

- CGI-S, I/PGI-S, I

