3.6 Sample Size and Power

The study sample size (N) is predicated on primary endpoint as detailed above. For the analysis, primary endpoint as well as the secondary endpoints will be tested on the ITT & PP populations. Estimates of effect size for the various outcomes are shown below. Assuming the same effect sizes observed in PROSPECT (clinicaltrials.gov NCT03597100), at $p = 0.01$ we have the following results:

Metric	p value	N
Kinematic measurements for study duration of 2 weeks	0.01	40
Kinematic measurements for study duration of 4 weeks	0.01	30

Under these effect sizes, assuming up to 10% data attrition and with a paired difference test at 0.01 alpha against the null hypothesis of no change from baseline, the 34 to 50 subject analysis provides 90% power for testing of the primary endpoint.

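### The primary tremor window is centred on the pre-stimulation peak only, so random frequency shifts push the pre/post ratio above 1 without any change in tremor; the written hypotheses also point the wrong way

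*SAP*

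**What the plan says.** SAP 3.3 builds the primary endpoint in three steps.

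- The session's tremor frequency is the point in 3-12 Hz where the power spectral density (PSD) of the "pre-stimulation accelerometry data is largest".
- Tremor power "is integral of the PSD of the tremor accelerometry data in the 3 Hz window centered on" that one frequency. The same window therefore serves both recordings.
- The session response is pre power divided by post power. The patient's value is the median over sessions, with at least 10 usable sessions required.

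The hypotheses are H_0: M_T ≥ 1 against H_A: M_T < 1, tested by Wilcoxon's signed-rank test. Success is a two-sided p below 0.05. A log transformation is mentioned only for descriptive summaries. Under SAP 3.4, the secondary endpoints are tested only if this endpoint is met.

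The only spectral quality rule is that recordings be "sufficiently free of motion artifact, as detected by excessive power outside the" 3-12 Hz band; no threshold is given. SAP 3.9 lists no alternative window and no summary of pre/post frequency agreement. Protocol 9.3 refers to tremor power without defining a window. SAP 2.1 describes the design: "This is a prospective, single-site, single-arm, non-significant risk study".

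**The concern.** The numerator is measured in a window centred on its own peak. The denominator is measured in a window centred on the other recording's peak. Suppose two recordings come from the same distribution. Swapping them should turn the ratio into its reciprocal, but here it does not, because the window moves with whichever recording is called pre.

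The resulting bias has one sign, since a shift up or down lowers post power only. A median over sessions does not remove it, and neither do more sessions. The out-of-band filter does not catch it, because a shift from 5 to 6 Hz stays inside 3-12 Hz. There is no control arm in which it would cancel. This ratio alone decides whether the study succeeds and whether the secondary endpoints are tested.

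The hypotheses have a separate fault. With pre in the numerator, less tremor after stimulation gives a ratio above 1. The written alternative, M_T < 1, describes more tremor, contrary to the objective stated in the same section.

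**Working it through.** **1. The plan's own figures.** SAP 3.6 gives N = 30 for "Kinematic measurements for study duration of 4 weeks" at 0.01 and states that "the 34 to 50 subject analysis provides 90% power for testing of the primary endpoint". With 10% attrition, 30/0.90 = 33.3, so 34, which reproduces the lower bound. The 90% power cannot be reproduced, because neither an effect size nor an SD is printed.

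**2. Implied between-patient SD.** N = 30, two-sided alpha 0.01 and 90% power imply a standardised effect of 0.748 (noncentral t). If the planning effect is a log ratio, SD = ln(true ratio)/0.748:

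- ratio 1.3: 0.262/0.748 = 0.35
- ratio 1.5: 0.405/0.748 = 0.54 (0.55 used below)
- ratio 2.0: 0.693/0.748 = 0.93

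The three ratios are assumptions.

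**3. Closed form for one fixed shift D.** Take a Gaussian peak of width w and equal total power before and after. The ratio is [Φ(1.5/w) − Φ(−1.5/w)] / [Φ((1.5−D)/w) − Φ((−1.5−D)/w)]. For w = 0.5 Hz and D = 1 Hz this is 0.9973/0.8413 = 1.19. For w = 0.3 / 0.5 / 0.8 Hz:

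- D = 0.5 Hz: 1.00 / 1.02 / 1.06
- D = 1.0 Hz: 1.05 / 1.19 / 1.28
- D = 1.5 Hz: 2.00 / 2.00 / 1.88

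**4. Simulation under no effect.** The assumptions are a 5.5 Hz tremor with spectral bandwidth 0.5 or 1.0 Hz plus white noise, 20 s recordings and Welch spectra. Each pair was used in both orders, so pre and post are exactly exchangeable. Frequency was drawn independently for each recording, so the SD of the pre-to-post shift is √2 times the per-recording SD: 0.3, 0.5 and 0.7 Hz become 0.42, 0.71 and 0.99 Hz.

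| SD of pre-to-post shift | Null ratio, SAP window | Sessions with peaks more than 1 Hz apart |
|---|---|---|
| 0 Hz | 1.00 | - |
| 0.42 Hz | 1.01-1.02 | 1-3% |
| 0.71 Hz | 1.05-1.08 | 12-15% |
| 0.99 Hz | 1.1-1.2 | 25-28% |

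A window from the average of the two spectra, each scaled to unit 3-12 Hz power, gave 1.00 throughout. A second spectral model gave 1.01-1.04 at 0.42 Hz and 1.07-1.14 at 0.71 Hz, so the figures depend on the model.

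**5. False benefit at a 0.71 Hz shift SD.** For a signed-rank test on log(M_T), P ≈ 1 − Φ(1.96 − √(0.955·N)·ln R/SD), where 0.955 is the test's efficiency for normal data. With N = 45 the root is 6.556. For R = 1.05 (ln 0.0488) and R = 1.08 (ln 0.0770):

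- SD 0.35: 1 − Φ(1.96 − 0.914) = 15%; 1 − Φ(1.96 − 1.442) = 30%
- SD 0.55: 1 − Φ(1.96 − 0.582) = 8%; 1 − Φ(1.96 − 0.918) = 15%
- SD 0.93: 1 − Φ(1.96 − 0.344) = 5%; 1 − Φ(1.96 − 0.543) = 8%

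Full simulation gave 9-13% at SD 0.55 and 6% at the low end for SD 0.93. The range is therefore about 6-30% against 2.5%. At 0.42 Hz (R = 1.01-1.02) the same formula gives about 3-6%.

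**6. Test scale.** If the signed-rank test is run on M_T − 1 without logs, a lognormal M_T with true median 1 and SD 0.55 gives about 11% false benefit at N = 45 with no frequency shift at all. The rates in step 5 apply only to the log-scale test.

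**The case against.** The best defence is that nothing in the documents shows the triggering condition. The recordings in a session use a postural hold by the same patient, before and after 40 minutes of stimulation. The device design presumes a stable frequency: Protocol 2.1.2 has stimulation alternate at the subject's "tremor frequency (4 - 12 Hz), which is measured during a calibration procedure", and SAP 2.1 says that calibration "sets the stimulation burst frequency based on the measured tremor frequency". A 3 Hz window is wide enough to absorb shifts of a few tenths of a hertz. All of this stands. It limits the size of the bias but does not remove the asymmetry, and presuming stability is not measuring it.

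The planning SD is also weakly grounded. SAP 3.6 borrows its effect from another study and describes a paired difference test, not a median log ratio. The rates in the working are therefore illustrations, not error rates of the plan as written.

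A reader might infer three stronger things that the documents do not support:

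- **That a 0.5 Hz pre-to-post shift is already serious.** It is not: the closed form gives 1.00-1.06. A spread of 0.5 Hz in each recording is a different quantity, equal to a shift SD of 0.71 Hz.
- **That false benefit approaches certainty at moderate shifts.** That needs between-patient variation far below the 0.35-0.93 implied by the plan's own sample size.
- **That sessions without a clear peak are a second main source.** In simulation, excluding recordings with over 60% of power out of band removed 98% of such sessions and left a ratio of about 1.01. The SAP's threshold is unstated, so this can be neither claimed nor ruled out.

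**Conclusion.** The point holds in conditional form. SAP 3.3 does not treat the two recordings alike, nothing elsewhere in the plan corrects this, and the bias runs towards apparent tremor reduction. It is negligible at a shift SD of about 0.4 Hz, material at about 0.7 Hz and larger at 1.0 Hz. These sizes rest on assumed peak shape, noise and recording length, and on a log-scale test. Which case applies cannot be told from the plan, because no shift is given and no report of frequency agreement is planned. It would be wrong to conclude that the trial's result will be biased; large shifts are possible but not shown.

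The direction of the hypotheses is a definite error and does not depend on any assumption. Nor does it rescue the window: read literally, the bias runs away from the written H_A, but success is declared on a two-sided p-value, and the evident intent is that a ratio above 1 means improvement.

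The window rule should be changed before analysis. Confidence in the size is medium.

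**What to change.** 1. **Hypotheses and test scale.** Write H_0: M_T ≤ 1 against H_A: M_T > 1, or redefine the ratio as post/pre and keep the present signs. State that the signed-rank test is on log(M_T).
2. **Window.** Use one rule per session that treats both recordings alike, for example the peak of the average of the pre and post spectra after each is scaled to unit 3-12 Hz power. The scaling matters: an unscaled average also holds the null at 1.00, but is drawn towards the pre recording when tremor truly falls. Centring each recording on its own peak is an acceptable alternative. Keep the present definition as a sensitivity analysis.
3. **Reporting.** Give the distribution of the pre/post peak-frequency difference and the share of sessions with peaks more than 1 Hz apart. State the threshold for excessive out-of-band power.

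The cost is SAP wording and reprocessing of the kinematic data that Protocol 2.1.4 says may be stored, provided that recordings or spectra are kept and not only summary values. No visit or procedure changes.

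The reported response will be slightly smaller if frequency shifts. With a true ratio of 1.5, the present window overstates the response by 0.01-0.03, 0.08-0.10 and 0.21-0.29 at shift SDs of 0.42, 0.71 and 0.99 Hz; the scaled average stays within 0.02. Simulated power at N = 34 and SD 0.55 is 95-97% with the scaled average, against 97-100% with the present window.

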9.3 Primary Effectiveness Endpoints Analyses

Primary endpoint for the study is defined as within subject comparison of tremor power before stimulation to after stimulation. Statistical testing of the primary endpoint will be

A study of safety and efficacy of Transcutaneous Afferent Patterned Stimulation (TAPS) for reduction of action tremor in Parkinson's Disease (PD)	Protocol PD-02
	Rev A; 1-OCT-2020

based on the cohort of all enrolled and treated subjects for whom outcome data are available.

The statistical objective related to the primary endpoint is to demonstrate that Parkinson's disease action hand tremor is reduced from pre-stimulation values at baseline to post-stimulation values at 4 weeks, under treatment with the Cala Trio device. Formally, the null and alternative hypotheses to be tested for each primary endpoint are as follows:

$$H_0: \mu_T \geq 0$$

$$H_A: \mu_T < 0$$

where μ_T is the change from pre-stimulation at baseline to post-stimulation at 4 weeks in the endpoint in question.

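### The SAP's primary alternative hypothesis is reversed: on a pre/post ratio, M_T < 1 means tremor increased, so the success rule as written can only be met by worsening

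*SAP*

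**What the plan says.** SAP 3.3 builds the primary endpoint in steps. The single-session kinematic response "is defined as the pre-stimulation tremor power divided by the post-stimulation tremor power". The primary endpoint "is defined as the per-patient median of single-session kinematic responses", and the parameter tested, M_T, "is the median kinematic response captured over the 4-week study". The purpose of the test "is to demonstrate that action hand tremor severity in PD is reduced with the Cala Trio device".

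The hypotheses are H0: M_T ≥ 1 and H_A: M_T < 1. Testing "will be performed using Wilcoxon’s signed-rank test". The endpoint is met at a two-sided p-value below 0.05, "such that the null hypothesis is rejected in favor of the alternative hypothesis", and meeting it makes the study a success. SAP 3.4 allows the secondary endpoints to be tested only if the primary is met.

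Protocol 9.3 uses a different scale. Its parameter mu_T "is the change from pre-stimulation at baseline to post-stimulation at 4 weeks in the endpoint in question", with H0: mu_T ≥ 0 and H_A: mu_T < 0.

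**The concern.** When the ratio is pre over post, less tremor after stimulation pushes it above 1. The SAP's alternative covers values below 1, where post-stimulation power exceeds pre-stimulation power. The formal claim the study sets out to establish is thus the opposite of its stated aim.

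This is the study's decision rule. Applied literally, an effective device cannot succeed and its secondary endpoints may not be tested, while a device that worsens tremor can succeed and open the secondary hierarchy. The hierarchy does not restore direction further down, because the secondary alternatives in SAP 3.4 are non-directional (mu_T ≠ 0).

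Timing matters too. The study is single-arm and unblinded (Protocol 3.7), and sponsor staff analyze the data (Protocol 7.1). Reversing the primary hypothesis once results are known would be a post hoc change to the main criterion, however obvious the intent.

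**Working it through.** **1. Direction of the ratio.** With R = pre/post (SAP 3.3):

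- Tremor power halved: pre = 2, post = 1, so R = 2/1 = 2. This lies in H0 (M_T ≥ 1).
- No change: R = 1. This lies in H0.
- Tremor power doubled: pre = 1, post = 2, so R = 1/2 = 0.5. This lies in H_A (M_T < 1).

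Taking a per-patient median, and then a median over patients, does not alter the direction.

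**2. Comparison with the protocol.** On the protocol's difference scale the change is post − pre. Halving gives 1 − 2 = −1, which is below 0 and so lies in the protocol's H_A, as it should. A less-than sign is right for post − pre or for post/pre, and wrong for pre/post.

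**3. Other definitions.** No other SAP text redefines the ratio as post/pre, and SAP 3.9 refers back to 3.3. The definition is given in words and both inequalities are reversed together, so a misread symbol is an unlikely explanation. The only change listed for SAP revision B concerns the tasks in the secondary endpoints.

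**4. The plan's sample size.** SAP 3.6 gives N = 30 for 4 weeks at 0.01, with up to 10% attrition. 30/0.9 = 33.3, rounded up to 34, which matches the lower end of the stated 34 to 50. The N = 30 itself cannot be reproduced, because no effect size or SD is stated.

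**5. Implied effect and what it means for the rule.** Assumptions: the 90% power belongs to N = 30, alpha 0.01 is two-sided, and a paired t-test stands in for the signed-rank test. Solve for d in

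P(T > t_{0.995, 29}) = 0.90, where T is noncentral t with 29 df and noncentrality d√30.

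This gives d = 0.748. At the SAP's two-sided 0.05 level with n = 30:

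- Probability of rejecting toward benefit (ratio above 1): 0.977.
- Probability of rejecting toward the written H_A (ratio below 1): about 1.5 × 10⁻⁹, in practice zero.

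**6. Simulation with the planned test.** Signed-rank test of log(pre/post) against 0. Assumed, because the documents do not give them: n = 30 or 45, normally distributed log ratios with between-subject SD 0.6 or 1.0, 2,000 runs per setting. Success is two-sided p < 0.05 in the required direction; ranges are across the four settings.

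| True effect on tremor power | pre/post | Success, rule as written | Success, direction corrected |
|---|---|---|---|
| Halved | 2 | 0% | 95–100% |
| Cut by a third | 1.5 | 0% | 56–99% |
| None | 1 | about 2.5% | about 2.5% |
| Up by half | 0.67 | 54–99% | 0% |
| Doubled | 0.5 | 95–100% | 0% |

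**The case against.** The strongest reply is that the intent is plain. The sentence before the hypotheses speaks of reduced tremor, SAP 3.9 evaluates the device for reducing symptoms, and the protocol's sign is right on its own scale. This is very probably a drafting slip, and a sensible analyst would read it correctly. That is fair as to intent, and nothing here suggests that the sponsor would report worsening as success. But a SAP exists to fix the success criterion in advance, and the one it fixes is reversed.

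A second point is that the two-sided p-value has no direction, so a beneficial result would still give p < 0.05. That holds only if the clause requiring rejection in favor of the alternative is ignored, and then significance in either direction would pass. Neither reading confines success to reduced tremor. Pairing two-sided 0.05 with a required direction is not itself a fault: it amounts to a one-sided test at 0.025, and SAP 3.1 allows both forms.

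A third point is that the very small probability in step 5 looks more precise than its inputs allow. This stands. The figure should be read as zero, and the reversal follows from the algebra whatever the effect size.

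A fourth is that reversing the sign leaves the test scale open. SAP 3.3 mentions the log only for descriptive summaries. Under no effect (median ratio 1, lognormal ratios, log-SD assumed 0.6 or 1.0, n = 30), a signed-rank test on the raw ratio minus 1 gave significance in the benefit direction roughly 8% to 16% of the time, against about 2.5% on the log ratio. This is a separate issue and does not weaken the present point, but it is best settled in the same edit.

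**Conclusion.** The primary decision rule is wrong as written. SAP 3.3 places tremor reduction in the null hypothesis and tremor increase in the alternative, and defines study success as rejection toward the latter. This follows from the SAP's own definitions and needs no assumption.

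The size of the effect is total: under any real benefit the written rule has practically no chance of success, whereas the same data would meet a correctly directed rule about 97.7% of the time at the effect implied by the planning figures. That percentage rests on the back-solved effect and the t-test stand-in; the conclusion does not. That the sign was carried over from the protocol's change score is a plausible explanation but only an inference. The sample size is unaffected, because the power calculation is symmetric in sign. This must be corrected before the analysis.

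**What to change.** Change SAP 3.3 in one of two ways:

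- keep pre/post and write H0: M_T ≤ 1 against H_A: M_T > 1; or
- redefine the single-session response as post/pre and keep H0: M_T ≥ 1 against H_A: M_T < 1.

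In either case, restate the success rule as one-sided p < 0.025 in the direction of benefit, or two-sided p < 0.05 with the estimated response on the benefit side of 1. In the same edit, state that the signed-rank test is applied to the log of each patient's kinematic response against 0. Check that the definition in 3.3 and the summary in 3.9 then agree.

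The cost is a few lines of SAP text and a version entry. Data collection, conduct and sample size do not change. The revision should be dated before the primary endpoint data are examined.

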9.6 Planned Analyses

All participants in this study will be using the same device as the commercial users of Cala Trio diagnosed with ET, with a common user interface workflow. As with all commercial users, an accelerometer on the device will measure tremor power before and after a subset of 40-minute therapy sessions (every session for the first 40 sessions, followed by every 7th session thereafter). Subject-reported ratings of the therapy sessions (improved, no change, worsened) will be recorded after the acceleration measurements on the device.

A study of safety and efficacy of Transcutaneous Afferent Patterned Stimulation (TAPS) for reduction of action tremor in Parkinson's Disease (PD)	Protocol PD-02
	Rev A; 1-OCT-2020

The analysis will evaluate de-identified data from up to 50 subjects who complete Cala Trio therapy sessions during 4 weeks of at-home use. Subjects will be given instruction on how to calibrate the device's stimulation to their hand tremor frequency and will be instructed to use the therapy twice daily at home. Therapy efficacy will be quantified using improvement in tremor power pre- and post- stimulation. Tremor severity will be visually rated for all subjects by an expert rater according to UPDRS and the ADL score will be noted.

Formal analyses of the primary and secondary endpoints will be conducted after completion of study. It will take place once 50 subjects have reached the 4-week visit, at which time analyses subgroups of interest will also be investigated, tabulated and reported.

Study hypotheses will be tested for p-values of 0.05 and 0.01.

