 - Median kinematic improvement for each patient's high ($\geq 75^{\text{th}}$ percentile), medium ($25^{\text{th}} - 75^{\text{th}}$ percentile) and low ($\leq 25^{\text{th}}$ percentile) pre-stimulation tremor
 - Of sessions that started with patient-specific "high" tremor, % sessions that had $\geq 0\%$ and $\geq 50\%$ reduction in tremor (i.e., rate of tremor "relief")
 - Of sessions that started with patient-specific "low" tremor, % sessions that ended in "low" tremor (i.e., rate of tremor "prevention")
- Average change in tremor power 1st, 2nd, 3rd and 4th weeks
- Correlation between log-transformed median pre-stimulation tremor power in first subset of days (e.g., 7, 14) compared to analogous data from final subset of days
- Correlation between log-transformed median kinematic response in first subset of days (e.g., 7, 14) compared to analogous data from final subset of days
- Summary of available BF-ADL scores based on recall at Visit 1, and 1st, 2nd, 3rd and 4th weeks
- Device usage metrics

These exploratory endpoints will be summarized and reported descriptively. Any hypothesis testing will be performed according to the general principles defined in this document.

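### SAP 3.3 sets no scale for the primary signed-rank test: on raw power ratios neither tail holds 2.5%, and which tail counts as success is itself contradictory

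*SAP*

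**What the plan says.** SAP 3.3 builds the primary endpoint in three steps.

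- The single-session response "is defined as the pre-stimulation tremor power divided by the post-stimulation tremor power", so a value above 1 means tremor fell.
- The patient-level endpoint "is defined as the per-patient median of single-session kinematic responses". No log is taken at either step.
- The null boundary for M_T is 1 and the alternative is M_T < 1. The stated aim is to "demonstrate that action hand tremor severity in PD is reduced with the Cala Trio device", which for this ratio means M_T > 1.

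On the test, the SAP says "Hypothesis testing of the change score M_T will be performed using" Wilcoxon's signed-rank test. Success needs a two-sided p below 0.05 with rejection in favour of the alternative, which is 2.5% in the relevant tail.

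Within 3.3, logs appear only where the endpoint is to be "summarized descriptively using log-transformed mean and standard deviation, median, and interquartile range". The other uses are exploratory, for example "Correlation between log-transformed median kinematic response in first subset of days" in SAP 3.9. Protocol 9.3 does not settle the matter. It describes a different quantity, a change from baseline pre-stimulation to week-4 post-stimulation, with a negative alternative.

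**The concern.** The signed-rank test is valid for a null value when the data are symmetric about that value. A ratio of two positive quantities with median 1 is generally not symmetric about 1. Halving tremor gives pre/post = 2, a deviation of +1.0. Doubling it gives 0.5, a deviation of −0.5. Improvements of the same proportional size therefore receive larger ranks than worsenings.

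Two consequences follow. Under no effect, the tail above 1 rejects too often and the tail below 1 too rarely. The p-value also changes if the same data are written post/pre.

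The second consequence matters here because the SAP contradicts itself on the direction of the ratio. This one test decides study success and, under SAP 3.4, opens testing of all eight secondary endpoints. The trial is single-arm and unblinded, so no concurrent control would expose a marginal false positive.

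**Working it through.** **Inputs from the documents.** The sample-size tables give N = 30 for 4 weeks and N = 40 for 2 weeks, with up to 10% attrition and 34 to 50 subjects (Protocol 9.7, SAP 3.6). At least 10 valid sessions per patient are required (SAP 3.3). Home use is twice daily for 28 days: 2 × 28 = 56 sessions. Protocol 9.6 describes motion recording at "every session for the first 40 sessions, followed by every 7th session thereafter".

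**The plan's own figures.** 30/0.9 = 33.3, which rounds up to the stated 34. 40/0.9 = 44.4, which rounds up to 45, so 50 is not the inflated 40. The 90% power cannot be recomputed, because neither document gives an effect size or SD. Working backwards, 90% power at alpha 0.01 with N = 30 needs a standardized paired effect of about 0.66–0.75, depending on sidedness and on a normal or t calculation.

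**Assumption.** The SD of log M_T between patients is not given, so it is varied. Under no effect, pre and post are taken as exchangeable, so log(pre/post) is symmetric about 0.

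**Check 1, patient level.** Simulate M = exp(sZ) with Z standard normal. Rank |M − 1| for the raw test and |log M| for the log test, with 2.5% per tail and n = 45 (50 × 0.9). There were 40,000 trials per cell.

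| SD of log M_T | Raw, tail above 1 | Raw, tail below 1 |
|---|---|---|
| 0.05 | 2.8% | 2.1% |
| 0.1 | 3.4% | 1.6% |
| 0.2 | 4.8% | 1.2% |
| 0.3 | 6.2% | 0.8% |
| 0.54 | 10.9% | 0.4% |
| 0.92 | 20.4% | 0.2% |

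On the log scale both tails are 2.3–2.6% in every cell. With exact critical values and 100,000 trials, N = 34 gives 3.2% above and 1.8% below at SD 0.1, and 8.4% and 0.6% at SD 0.5. N = 50 gives 3.6% and 1.7%, then 11.1% and 0.5%.

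**Check 2, session level, no true patient differences.** The spread of M_T is then session noise only. The SD of a median of m log-ratios is about 1.253 × (session SD)/√m:

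- session SD 0.3, m = 56: 1.253 × 0.3/7.48 = 0.05
- session SD 1.0, m = 40: 1.253 × 1.0/6.32 = 0.20

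Simulated tails above 1 for n = 34 or 45 and session SD 0.3–1.0, with ranges spanning repeat runs:

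- 40–56 sessions: 2.5–5.3%
- 20 sessions: 2.4–6.9%
- 10 sessions for every patient: 3.6–12.9%

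Taking the log after the raw median leaves up to 4.5% at 10 sessions, because an even count averages the two middle ratios on the raw scale. Taking the log of each session first gives 1.7–2.9% throughout.

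**Check 3, direction.** In one simulated data set (n = 45, log mean 0.15, log-SD 0.54) the two-sided p-value is 0.009 as pre/post, 0.109 as post/pre and 0.027 on logs. On the log scale, inverting the ratio only changes the sign, so the two-sided p-value stays the same.

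**Check 4, power for benefit at n = 45.**

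| Log-SD | True pre/post ratio | Standardized effect | Raw pre/post | Log | Raw post/pre |
|---|---|---|---|---|---|
| 0.54 | 1.25 | 0.223/0.54 = 0.41 | 92% | 75% | 45% |
| 0.54 | 1.5 | 0.405/0.54 = 0.75 | 100% | 99.8% | 97% |
| 0.92 | 1.5 | 0.405/0.92 = 0.44 | 97% | 80% | 35% |

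Part of the raw pre/post advantage is its inflated error rate.

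**The case against.** The best reply is that the scale is unstated rather than wrong. The sentence before the test asks for a log-transformed mean and SD, and an analyst could reasonably test logs. That is true. But the null is written at 1 and logs are confined to descriptive and exploratory text, so a programmer following SAP 3.3 would rank raw ratios. The primary test should not rest on inference.

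Second, on the literal hypotheses the success tail is the one below 1, which is conservative, so no inflation follows from the text as written. This is correct, but that tail is the worsening side for a pre/post ratio. The contradiction has to be repaired, and either repair leaves a scale problem.

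Third, the large figures need real differences between patients. A device with no effect in anyone gives an SD of log M_T of only about 0.05–0.20 at 40–56 sessions. Rates of 10.9% or 20.4% require many patients to worsen and as many to improve, balanced on the log scale. This stands, and 2.5–5% is the better guide under a strict no-effect null. The 10-session range likewise assumes that every patient sits at the inclusion floor. With counts spread over 10–56 the upper tail is 2.9–4.9%, and logging after the median is then nearly as good as logging before it.

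Fourth, at effects near the implied design value of about 0.7 the two scales almost always agree. This also stands; the scale matters for smaller effects.

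**Conclusion.** The concern holds. SAP 3.3 does not put the primary test on the log scale. On the literal raw-ratio reading, one tail exceeds 2.5% and the other falls short.

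If the pre/post ratio is kept and the alternative corrected, the success tail is liberal: about 2.5–5% under a strict no-effect null with near-complete session data, and more with few sessions or true patient heterogeneity. If the alternative is kept and the ratio inverted, the success tail is conservative and power is lost.

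The result rests on pre and post being exchangeable under no effect. If raw ratios were symmetric about 1, the raw test would hold its level. The size rests on an SD that the documents do not give; near 0.1 it is small. This should be fixed before analysis. Confidence in the mechanism is high; confidence in its size in this trial is moderate.

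**What to change.** Rewrite the endpoint and test text in SAP 3.3 as one edit:

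- Define each patient's kinematic response as the median, over qualifying sessions, of log(pre-stimulation power / post-stimulation power), with logs taken before the median.
- Test it by Wilcoxon signed-rank against 0, with H0: median ≤ 0 and HA: median > 0, so that reduction is positive.
- Declare success on a two-sided p below 0.05 with the estimate above 0.
- Report the Hodges–Lehmann estimate and 95% confidence interval, back-transformed to a ratio.

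The cost is one SAP paragraph and one line of code, with no new data. The benefit p-value will usually be less favourable than on raw pre/post ratios. Apparent power falls where effects are small relative to patient spread (92% to 75% in the first row of the power table) and hardly at all at a ratio of 1.5 with log-SD 0.54. Correcting the inequalities alone would leave the scale problem in place.
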